8.2.8 Assessment of local reactogenicity - Investigator tasks

Investigators will assess acute local reactogenicity at the visits given in the SoA (Section 1.3).

Investigators will grade and record acute local reactions as described in Section 8.2.6.1. If any acute local reactions meet any SAE criteria, they must be recorded as an SAE.

8.2.9 Subject hotline

Trial subjects will be provided with contact details for a Subject hotline, which can be used to contact the trial site during their participation in the trial should they require guidance or should they experience any symptoms of illness. The reporting of any symptoms of illness, e.g., flu-like symptoms, may trigger diagnostic measures (including *ad hoc* site visits) at the discretion of the investigator.

For guidance on the handling of specific adverse reactions, see Section 8.5.

8.2.10 Wellbeing phone calls

Subjects will be contacted by phone for non-leading wellbeing calls at the times given in the SoA (Section 1.3). Subjects will additionally be contacted by phone 14 d post-IMP administration to solicit potential delayed injection site reactions, as given in the SoA (Section 1.3). During this phone call, they will be asked to report on any new skin reaction at the site of injection in the last 7 d prior to the phone call (Day 8 to Day 14 post IMP-administration).

8.3 Adverse events and SAEs

Definitions of AEs and SAEs can be found in Section 10.4.

Page 48 of 82 Version: 4.0 Date: 13 FEB 2023

8.3.1 Time period and frequency for collecting AE and SAE information

All AE and SAE information will be collected at the time points specified in the SoA (Section 1.3).

Non-serious AEs will only be collected as of first IMP dose administered while SAEs need to be recorded upon awareness starting once informed consent is given.

Adverse events and medically attended adverse events will be collected until 28 d after each dose and SAEs need to be recorded continuously until Visit 14 (52 weeks post-Dose 3).

Medical occurrences that begin after obtaining informed consent but before the start of trial treatment administration must be recorded on the respective Medical History/Current Medical Conditions section of the CRF and not in the section of the AE unless they qualify as SAEs.

Medical occurrences meeting the criteria for an SAE (see Section 10.4.2) must be reported as SAEs (see Section 8.3.4).

8.3.2 Detecting and reporting AEs and SAEs

The investigator and any qualified designees are responsible for detecting, documenting, and reporting events that meet the definition of an AE or SAE and remain responsible for following up all AEs and SAEs. The investigator will record on the CRF all observed directly and all spontaneously reported AEs and SAEs reported by the trial subject.

Open-ended and non-leading verbal questioning of the trial subject is the preferred method to inquire about AE occurrences. Care will be taken not to introduce bias when detecting AEs and/or SAEs.

Guidance for the recording, evaluating, and assessing of AEs and SAEs is provided in Section 10.4.

The US FDA "Toxicity Grading Scale for Healthy Adult and Adolescent Volunteers Enrolled in Preventive Vaccine Clinical Trials" will be used to grade the severity of AEs and SAEs.

Investigators are not obligated to actively seek AEs or SAEs after conclusion of the trial participation. However, if the investigator learns of any SAE, including a death, at any time after a trial subject has been discharged from the trial, and he/she considers the event to be related (see Section 10.4, for guidance the assessment of causality) to the trial treatment or trial participation, the investigator must promptly notify the sponsor as described in Section 10.4.4.

The sponsor may request that the investigator obtain specific follow-up information in an expedited fashion.

All SAEs (initial and follow-up reports) will be recorded and reported to the sponsor or designee within 24 h after the site becomes aware of the event, as indicated in Section 10.4.4.

Clinical Trial Protocol Trial number: BNT165-01 Page 49 of 82 Version: 4.0 Date: 13 FEB 2023

For real time monitoring of events which may contribute to the pausing rules criteria, all such AEs (Grade 3 or higher possibly related) need to be reported on an expedited timeline (within 24 h) like that of an SAE.

8.3.3 Follow-up of AEs and SAEs

After the initial AE/SAE report, the investigator is required to proactively follow each trial subject at subsequent visits/contacts.

All AEs and SAEs will be followed until resolution, stabilization, the event is otherwise explained, or the trial subject is lost to follow-up, or the trial subject withdraws consent (as defined in Section 7.3). If no final status is reached by the End of Trial Visit, the investigator must confirm the unavailability of a final status. Further information on follow-up procedures is provided in Section 10.4.2.

The investigator is obligated to perform or arrange for the conduct of supplemental measurements and/or evaluations as medically indicated or as requested by the sponsor to elucidate the nature and/or causality of the AE or SAE as fully as possible. This may include additional laboratory tests or investigations, histopathological examinations, or consultation with other health care professionals.

New or updated information will be recorded in the originally completed CRF.

If a trial subject dies during participation in the trial or during a predefined follow-up period (see the SoA in Section 1.3), the investigator will provide the sponsor a copy of any postmortem findings including histopathology.

The investigator will submit initial and follow-up AE/SAE reports to the sponsor within 24 h of receipt of the information, as indicated in Section 10.4.4.

All ongoing AEs/SAEs will be followed until resolution, considered by the investigator to be stable or chronic (resolved with sequelae), the trial subject is lost to follow-up, or the trial subject withdraws consent. If no final status is reached by the End of Trial Visit, the investigator must confirm the unavailability of a final status.

8.3.4 Reporting requirements for SAEs including suspected unexpected serious adverse reactions (SUSARs)

Prompt notification of an SAE via an EDC system and the provided paper SAE form by the investigator to the sponsor within 24 h of the site's awareness is essential so that the ethical responsibilities to trial subjects, the safety standards of a trial treatment under clinical investigation, and regulatory reporting obligations can be met.

The sponsor has a legal responsibility to notify both the local regulatory authority and other regulatory agencies involved in the conduct of trials with the same IMP about the safety of a trial treatment under clinical investigation. The sponsor will comply with country-specific regulatory requirements relating to safety reporting to the regulatory authority, Institutional Review Boards (IRBs)/Independent Ethics Committees (IECs), and investigators. The execution of reporting to the different entities may be delegated as detailed in the trial-specific Safety Management Plan.

Clinical Trial Protocol Trial number: BNT165-01 Page 50 of 82 Version: 4.0 Date: 13 FEB 2023

All serious adverse reactions, the nature, severity or outcome of which is not consistent with the reference safety information are "unexpected serious adverse reactions". The expectedness assessment for all related SAEs is based on the reference safety information included in Section 6.1.5 of the BNT165 IB.

All suspected adverse reactions related to an IMP that occur in this trial, and that are both unexpected and serious qualify as SUSARs. SUSARs are subject to expedited reporting requirements according to applicable regulatory requirements and guidance (i.e., ICH E2A guidance). SUSARs are subject to expedited reporting following ICH E2A standard. Information about Analysis of Similar Events will be added to the SUSAR report. IRBs will receive SUSAR reports as applicable.

For the IMPs, it is the sponsor's or delegate's responsibility to perform expedited SUSAR reporting submission to the applicable regulatory authorities, the IRB/IECs within the timelines stipulated in the respective country regulations. Reporting to the investigators will follow country-specific regulatory requirements and applicable guidelines.

8.3.5 Pregnancy testing and handling of pregnancies

For VOCBP, pregnancy tests and counselling will be performed at the times given in the SoA (Section 1.3).

For all trial subjects, pregnancy information will be collected over the time period defined in SoA (Section 1.3).

Any female trial subject who becomes pregnant while participating in the trial will need to discontinue the IMP immediately.

Pregnancy information will only be collected after obtaining written informed consent from the pregnant female trial subject (or if a male trial subjects' partner becomes pregnant, written informed consent from the trial subjects' partner).

If a pregnancy is reported, the investigator should inform the sponsor within 24 h of learning of the pregnancy and should follow the procedures outlined in Section 10.5.3.

Pregnancy *per se* is not an AE (and hence not an SAE). Abnormal pregnancy outcomes (e.g., spontaneous abortion, fetal death, stillbirth, congenital anomalies, ectopic pregnancy) are considered SAEs.

8.3.6 Death events

Any death that occurs within the observation period will be reported as an SAE, if not covered by the exemptions to the SAE definition as defined in Sections 8.3.7, 10.4.2, and 10.4.2.2, which do also apply for fatal cases. Date and cause of death will be recorded. If available, a copy of an autopsy report should be submitted if available upon request.

In case of a fatal event, the event term should not be "death" but the underlying event which led to death (death = outcome). If there is more than one AE in a fatal case, only for the AE leading the outcome "fatal" (death) should be selected. If the cause of death is unknown and cannot be ascertained at the time of reporting, "unexplained death" should be documented as event term.

Page 51 of 82 Version: 4.0 Date: 13 FEB 2023

In addition to reporting as SAE, the death page of the CRF needs to be completed.

8.3.7 Disease-related events/outcomes not qualifying as AEs or SAEs Not applicable.

8.3.8 Adverse events of special interest

No AEs of special interest are defined for this trial.

8.4 Actions in case of overdose or error in drug administration

For a definition of an overdose, see the subsection "AEs associated with an overdose or error in drug administration" in Section 10.4.1.3.3.

The sponsor does not recommend specific treatment for an overdose.

In the event of an overdose or an error in drug administration, the investigator should:

- Contact the trial Medical Monitor immediately.
- (At the discretion of the investigator) Give symptomatic treatment.
- Closely monitor the trial subject for any AE/SAE and laboratory abnormalities (at least 7 d).
- Document the quantity of the excess dose as well as the duration of the overdose in the CRF.

Decisions regarding dose interruptions or modifications will be made by the investigator in consultation with the trial Medical Monitor based on the clinical evaluation of the trial subject.

8.5 Treatment for specific adverse reactions

Expected adverse reactions are mostly reflective of mild to moderate local and systemic reactogenicity events. Additionally, anaphylaxis can occur after any vaccination. For further details see the BNT165 IB.

8.5.1 Myopericarditis

Any subject who reports acute chest pain, shortness of breath, palpitations, or any other symptom(s) that might be indicative of myocarditis or pericarditis within 6 weeks after an IMP dose must be specifically evaluated by a cardiologist for possible myocarditis or pericarditis.

The same applies for any subject in whom a new ECG abnormality (compared to baseline) consistent with probable or possible myocarditis or pericarditis or abnormal Troponin I level is observed within 6 weeks after each IMP dose administration. In addition to a clinical evaluation, the following should be performed:

ECG and

Clinical Trial Protocol Trial number: BNT165-01 Page 52 of 82 Version: 4.0 Date: 13 FEB 2023

 Measurement of the Troponin I level, if not already obtained (for cases where the abnormal Troponin I level is the initial reason for evaluation).

If myocarditis or pericarditis is suspected based upon the initial evaluation, the following should also be performed:

- Cardiac echocardiogram and/or
- Cardiac magnetic resonance study

Any case of myocarditis, pericarditis or myopericarditis, that is assessed as possibly related by the investigator will constitute a trial treatment pausing rule per Section 7.1.1, until the IRC reviews the event. The ECG abnormalities consistent with probable or possible myocarditis or pericarditis are those judged as such by a cardiologist, including:

- Sustained atrial or ventricular arrhythmias
- Second-degree Mobitz Type II or worse atrioventricular block, new bundle branch block
- Diffuse ST-segment elevation or PR-segment inversion, compatible with pericarditis

The investigators must followup on any case of clinically significant ECG abnormality with troponins and other relevant tests till resolution. If there are such abnormal tests after the first dose, then investigators must make all relevant assessments before the second dose in reasonable time.

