- c Vital signs: systolic/diastolic blood pressure, pulse rate, respiratory rate, and oral body temperature.
- d Viral screen: screen for HIV 1, HIV 2, Hepatitis B, and Hepatitis C.
- e Clinical laboratory tests: (Chemistry) alkaline phosphatase, alanine transaminase, creatinine, c-reactive protein, albumin, amylase, aspartate transaminase, gamma glutamyl transpeptidase, total bilirubin, blood urea nitrogen, glucose, lipase, sodium, potassium, calcium, troponin, IgG, IgM and IgA; (Hematology) hemoglobin, hematocrit, red blood cell count, white blood cell count and differential (neutrophils, lymphocytes, monocytes, eosinophils, basophils), platelet count. Only in women who are not VOCBP (to confirm postmenopausal status): follicle stimulating hormone at Visit 0. Only for VOCBP: serum β-HCG at Visit 0.
- f On days with dosing, blood draws should be done pre-dose.
- g VOCBP: The serum β-HCG pregnancy test at Visit 0 is performed using the sample collected for clinical laboratory tests. Before each dosing, urine pregnancy tests will be performed using a commercial kit at the site and the trial subjects will be counseled about the need for consistent and correct use a highly effective method of contraception.
- h If justified by the collected data, the listed blood draw days and the draw volumes may be adapted if not increasing the total number of draw days or the total volume drawn. Leftover blood after completion of the immunogenicity assessments may be used for additional biomarker analyses.
- i Trial site personnel will remind the subjects to record the oral body temperature and the worst grade for each symptom in the e-diary at approximately the same time every evening on the day of IMP administration and then every day in the evening for a total of seven consecutive days. Ask/remind the subject to contact the site if they experience any severe or potentially life-threatening reactogenicity events.
- The AEs and MAAEs will be collected continuously until 28 d after each dose, and SAEs need to be recorded continuously until Visit 14.
- k Trial subjects will be contacted by phone for non-leading wellbeing calls at 5 h, 24±4 h (after Dose 3 only), and 48±4 h after each IMP dose.
- I Local reactogenicity assessed by the investigator pre-dose and up to 1 h after dosing.
- m 12-lead ECG will be performed pre-dose.
- n Subjects will make their last entries in the evening before the 7 d follow-up visit.

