7.1.1 Cohort trial treatment pausing rules

Grading scales for the intensity of AEs and SAE will be based on guidance from the US Food and Drug Administration "Toxicity Grading Scale for Healthy Adult and Adolescent Volunteers Enrolled in Preventive Vaccine Clinical Trials".

If any of the below is met in a given cohort and after any dose, no additional trial subjects will be assigned to the cohort and administration of trial treatment, including administration of Dose 2 and/or Dose 3 for affected cohorts and any higher DL(s), will be paused until the IRC reviews the event(s):

- Any SAE developed by subject administered with trial treatment (at any DL), for which there is no alternative, plausible, attributable cause and which is assessed by the investigator, or the sponsor as possibly related.
- Any severe (Grade 3) hypersensitivity or any anaphylactic AE that occurs within 7 d
 of vaccination without a clear alternative cause.

NOTE: Grade 3 hypersensitivity is defined as symptomatic bronchospasm with or without urticaria, parenteral intervention, allergy related edema/angioedema, or hypotension. Grade 4 hyposensitivity encompasses all life-threatening events and for which urgent intervention is indicated.

Clinical Trial Protocol Trial number: BNT165-01 Page 40 of 82 Version: 4.0

Date: 13 FEB 2023

- Any Grade 4 AE after administration of trial treatment (at any DL) that is assessed as possibly related by the investigator, or for which there is no alternative, plausible, attributable cause.
- Any case of immune-related AE, including but not limited to myocarditis, pericarditis or myopericarditis, that is assessed as possibly related by the investigator, or for which there is no alternative, plausible, attributable cause.
- Any case of fever >40.0°C (measured orally) persisting for over 6 h despite the use of antipyretics after administration of trial treatment (at any DL) that is assessed as possibly related by the investigator and/or sponsor, or for which there is no alternative, plausible, attributable cause.
- If two trial subjects develop the same or similar Grade 3 or higher AE at least possibly related to trial treatment (solicited injection site reactions, solicited systemic reactions, unsolicited AEs, and laboratory abnormalities considered at least possibly related to trial treatment).

NOTE:

- Reactogenicity e-diary data confirmed by the investigator as being entered by the subject in error will not contribute toward a pausing rule.

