8.5.4.1 Overall summary of adverse events

The number and percentage of subjects reporting the below events will be summarized for the subjects in safety set.

- Unsolicited AEs with onset from Day1 through Day 28 post IMP dose will be summarized for each dose (i.e., 1st dose, 2nd dose, 3rd dose) and regardless of the number of doses received. All events entered on the "Adverse Events" eCRF page with an onset date within the above-mentioned timeframe will be analysed. This includes solicited events that persisted beyond Day 7 after IMP administration or that qualified as an SAE. The following will be analysed:
 - Any unsolicited AEs
 - Related AEs
 - AE of grade >=3
 - Related AEs of grade >=3
 - Any solicited reactogenicity event that continues longer than 7 d post-IMP administration or is an SAE
 - Unsolicited AEs leading to withdrawal of IMP
 - Unsolicited AEs leading to study withdrawal
 - SAEs, with onset from Day 1 through Visit 14. The following will be analysed:
 - Any SAEs
 - Related SAEs
 - SAEs of grade >=3
 - Related SAEs of grade >=3
 - MAAE, with onset from Day1 through 28 days after each dose. The following will be analysed:
 - Any MAAEs
 - Related MAAEs

Page 24 of 36 Version: 3.0 Date: 08 MAY 2024

- MAAEs of grade >=3
- Related MAAEs of grade >=3

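### Possible myopericarditis is evaluated for 6 weeks after each dose, but required AE/MAAE recording and the general AE/MAAE tables stop at 28 days, leaving a narrow set of non-serious cases outside every AE table

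*Protocol*

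**What the plan says.** **Evaluation window.** Under Protocol 8.5.1, a subject who reports suggestive symptoms "within 6 weeks after an IMP dose must be specifically evaluated by a cardiologist". The same applies where a suggestive new ECG abnormality or an "abnormal Troponin I level is observed within 6 weeks after each IMP dose administration".

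**Recording window.** Protocol 8.3.1: "Adverse events and medically attended adverse events will be collected until 28 d after each dose". Footnote j of the schedule of activities (Protocol 1.3): "The AEs and MAAEs will be collected continuously until 28 d after each dose, and SAEs need to be recorded continuously until Visit 14".

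**Tabulation window.** SAP 8.5.4.1: "Unsolicited AEs with onset from Day1 through Day 28 post IMP dose will be summarized for each dose"; "MAAE, with onset from Day1 through 28 days after each dose"; and "SAEs, with onset from Day 1 through Visit 14". SAP 8.5.4.2 uses the same 28-day limit for its tables of all, related and non-serious AEs and of MAAEs. It also has two tables without that limit: AEs leading to IMP discontinuation and AEs leading to study withdrawal. The AE listings in SAP 8.5.4.4 carry no onset window.

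**Action rules.** The cohort pausing rule in Protocol 7.1.1 covers "Any case of immune-related AE, including but not limited to myocarditis, pericarditis or myopericarditis" if possibly related or without another plausible cause. It sets no time, grade or seriousness limit. Protocol 7.1.3 makes a suspected or confirmed, possibly related case a reason for permanent discontinuation of IMP. Protocol 8.3.8 defines no AEs of special interest.

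**The concern.** The protocol looks for one class of event over 6 weeks but requires AEs to be recorded over only 4. The event is one it takes seriously: it appears in the exclusion criteria, the pausing rule, the individual discontinuation rule and a section added in version 4.0 at FDA request (Protocol 10.8.3).

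Safety is the primary objective, and AEs and MAAEs are primary endpoints. A symptom that leads to an unscheduled cardiology visit would ordinarily meet the MAAE definition in Protocol 10.4.1. If it starts in the gap, however, nothing in Protocol 8.3.1 requires it to be recorded as one.

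With 16 vaccinees planned per cohort, one case is 1/16 = 6.25% of a dose level. A reader of the trial report who sees zero cases in the 28-day tables may take that zero to cover the whole 6-week evaluation period.

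**Working it through.** The plan states no figure on this point, so there is nothing to reproduce. The check is date arithmetic followed by tracing a case through the tables.

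**1. Length of the gap**

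- Evaluation window: 6 × 7 = 42 days (Protocol 8.5.1).
- Recording window: 28 days (Protocol 8.3.1).
- Gap per dose: 42 − 28 = 14 days, and 14/42 = 33%.
- Over three doses: 3 × 14 = 42 of 3 × 42 = 126 days per subject.
- SAP 8.1.1 counts the dose day as Day 1. The AE overview's Day 28 is then 27 days after the dose, and the tabulation gap is 42 − 27 = 15 days.

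**2. Position of the gap, for doses on trial Days 1, 57 and 183**

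| Dose | 28 d ends (dose day + 28) | 6 weeks end (dose day + 42) | Gap (trial days) | Next dose, earliest in window |
|---|---|---|---|---|
| 1 | 29 | 43 | 30–43 | 57 − 2 = 55 |
| 2 | 85 | 99 | 86–99 | 183 − 7 = 176 |
| 3 | 211 | 225 | 212–225 | none |

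**3. Where a case with onset in the gap can appear**

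- *Serious, any dose:* recorded and tabulated to Visit 14. Nothing is lost.
- *Non-serious, possibly related, after Dose 1 or 2:* outside the 28-day tables. A dose remains and Protocol 7.1.3 calls for discontinuation, so the case belongs in the study-long IMP-discontinuation table, provided it is on the AE page.
- *Non-serious, after Dose 3:* no dose remains to stop. Protocol 10.4.3 gives an event starting after the last administration as an example of a not-applicable action. The case enters no AE table unless the subject leaves the study.
- *Non-serious, judged unrelated, any dose:* Protocol 7.1.3 is not triggered. The case enters no AE table unless it leads to IMP discontinuation or study withdrawal.

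**4. Whether another route closes the gap**

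- There is no special-interest category and no separate myopericarditis table.
- ECG and clinical laboratory draws are scheduled only at screening, on dosing days and at 7 days. A troponin or ECG result from the gap is therefore unscheduled, and SAP 8.1 keeps unscheduled assessments out of summaries, though in the listings.
- The 24-hour notification in Protocol 7.1 and 8.3.2 covers possibly related events of Grade 3 or higher, so a Grade 1 or 2 case is not included.
- Protocol 10.4.2.2 asks for AEs after the observation period to be reported to the sponsor when a relationship is suspected. It does not mention a CRF entry and does not reach cases judged unrelated.

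**The case against.** The best defence is that an evaluation window need not equal a tabulation window. Section 8.5.1 sits under treatment of adverse reactions, the primary estimands are explicitly 28-day, and the SAP matches them. That stands as far as the estimands go, and there is no case for changing them.

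A reader might infer that a non-serious case in the gap can never enter an AE table, or that the SAP would drop it by onset date even if it were recorded. The documents do not support either. The IMP-discontinuation and study-withdrawal tables run for the whole study, and the AE listings have no onset limit.

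A reader might also infer that the pausing rule fails for want of an AE record. That is not supported either. Section 8.5.1 itself makes any possibly related case a pausing event, without requiring an AE-page entry or a 28-day onset. Investigators must raise safety concerns with the sponsor at once (Protocol 7), and the IRC may meet ad hoc on any signal (Protocol 7.1).

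Nor is the work-up invisible. Clinically significant results of laboratory tests outside the protocol go into the CRF (Protocol 8.2.4), as do abnormal ECG findings (8.2.3) and concomitant medication with its reason. A confirmed case may also be classed as an SAE on medical judgement (10.4.2).

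These points narrow the concern. None of them requires an AE term for a non-serious case in the gap, and none gives a summary over the 6 weeks.

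**Conclusion.** The mismatch is real and should be reconciled, but the loss is narrow. A non-serious case 29 to 42 days after a dose falls outside required AE/MAAE recording and the general AE/MAAE tables. If recorded, it can appear in the AE listings and, if it leads to IMP discontinuation or study withdrawal, in one of the two study-long tables. A non-serious case after Dose 3, or one judged unrelated after any dose, enters no AE table unless it has one of those two consequences.

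The size is 14 of 42 days per dose (15 on the SAP's day count for the AE overview). This is a share of calendar time, not of cases. The documents give no event rate or onset distribution, so no expected number of missed cases can be derived.

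The conclusion assumes doses on the planned days and investigators who record what Protocol 8.3.1 requires and no more. Serious cases and the pausing rule are not affected.

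**What to change.** 1. In Protocol 8.3.1 and footnote j, state that any event or finding that triggers Section 8.5.1 within 6 weeks after a dose is recorded on the AE page, regardless of seriousness or relatedness.
2. In SAP 8.5.4, add one separate table of these events by dose level and dose over the 6-week window. Leave the existing 28-day tables and primary estimands as they are. The clinical evaluation is not touched.

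Attribution to a dose stays clean: the extended windows after Doses 1 and 2 end on Days 43 and 99, before the earliest in-window next doses on Days 55 and 176.

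The cost is a short amendment and one extra table. No visit is added, since AE recording is already marked at Visits 5, 9 and 12, the first scheduled contacts after each gap.

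The weakness is recall. With the 28-day contact allowed at ±2 days, nothing is scheduled 31 to 42 days after a dose. The next visit comes 57 − 43 = 14 days after the window closes for Dose 1, 183 − 99 = 84 days (12 weeks) for Dose 2, and 84 − 42 = 42 days (6 weeks) for Dose 3. Capture would depend on subjects reporting promptly, for example through the existing hotline, or on what they remember at that visit.
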